9.4.2 ANALYSIS OF THE PRIMARY ENDPOINT(S)

For the primary outcome, if any missing data is identified, both negative and multiple imputation methods

will be used to estimate CRC screening completion. This approach to missing data was successfully used by Vernon and colleagues (Kinney et al, 2014; Steffen et al, 2015). Negative outcome imputation will assume that if there was no MRR-verified CRC screening, the procedure did not occur. Multiple imputation will be based on experimental condition, age at baseline, income, health insurance coverage, and any other covariates predictive of missingness in the imputation model. Twenty imputed datasets will be used to provide a combined estimate for missing values. We will employ SAS PROC MI and SAS PROC MIANALYZE, Version 9.4, to implement these imputation procedures. We will also conduct a complete case analysis including only those participants with a known primary outcome.

9.4.3 ANALYSIS OF THE SECONDARY ENDPOINT(S)

Linear regression will be used to assess secondary outcomes. All analyses will control for any confounding variables not managed through randomization (i.e., group difference $p < .10$). For the secondary outcomes, we will conduct multiple imputation for any missing data using the procedures described for the primary outcome.

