8.1 ENDPOINT AND OTHER NON-SAFETY ASSESSMENTS

This individually randomized, remote trial evaluates a mobile, video+SMS colorectal cancer (CRC) screening education program versus a standard-materials control. All study activities are conducted virtually; no study-specific physical exams, imaging, or biospecimen collection occur. Outcome verification uses medical record review (MRR) and self-report.

Screening, eligibility, and enrollment

- **Eligibility confirmation window.** Up to 30 days prior to enrollment. Site staff confirm basic eligibility from clinic records (e.g., age, overdue for CRC screening per guidelines, active phone number).
- **Consent & MRR authorization.** Participants complete electronic informed consent and provide HIPAA authorization for MRR.
- **Baseline survey.** Immediately post-consent, participants complete a baseline questionnaire.
- **Randomization.** After baseline completion, participants are assigned to intervention or control.

Interventions begin (initial administration conditions)

- **Intervention arm.** Participants receive an SMS link to the curriculum hub and proceed through brief, pre-recorded videos with tailored branches, followed by a post-education screening assistance (PESA) text sequence.
- **Control arm.** Participants receive text messages, some with links to standard educational materials via SMS. A working mobile number and ability to receive texts are required for delivery; there are no in-person or group sessions.

Measures and assessments (non-safety)

Baseline (pre-randomization)

- Demographics and contact details (mobile number required for delivery).
- CRC screening history (ever screened; modality and timing if applicable).
- Psychosocial measures (e.g., CRC knowledge; perceived risk/severity; perceived benefits/barriers for stool tests and colonoscopy; medical trust; self-efficacy).

During intervention (process/dose)

- Platform telemetry: timestamps for each SMS, link launches, chapter/video opens (percent viewed), assessment completions, participant replies (including keyword confirmations), and time in the assistance stream. These are used for exposure/dose summaries and adherence monitoring (not safety).

Follow-up (primary outcome window)

- **Primary outcome ascertainment:** Receipt of any guideline-concordant CRC screening within 6 months post-randomization, verified by MRR (test type, date, and result if available) and self-report.

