9.1 STATISTICAL HYPOTHESES

- Primary Endpoint(s):

We hypothesize that, compared to participants who receive standard educational materials via SMS (control), participants who receive the tailored mobile video+SMS intervention (m-CRCSi) will have a higher proportion completing any guideline-concordant colorectal cancer (CRC) screening within 6 months post-randomization. Alternatively, our null hypothesis is that there will be no difference between arms in screening completion at 6 months.

- Secondary Endpoint(s):

Self-reported proxy screening composite (6 months):

We hypothesize that the intervention arm will report a higher rate of any guideline-concordant CRC screening by 6 months than the control arm; the null hypothesis is that there will be no difference between arms.

CRC knowledge (baseline→6 months):

We hypothesize that intervention participants will show greater improvement in CRC knowledge from baseline to 6 months than control participants; the null hypothesis is that there will be no difference in change between arms.

Perceived susceptibility and severity (baseline→6 months):

We hypothesize that intervention participants will report greater increases in perceived susceptibility and severity from baseline to 6 months than control participants; the null hypothesis is that there will be no difference in change between arms.

Perceived benefits and barriers for colonoscopy and stool testing (baseline→6 months):

We hypothesize that intervention participants will report greater increases in perceived benefits and greater decreases in perceived barriers from baseline to 6 months than control participants; the null hypothesis is that there will be no difference in change between arms.

Medical trust (baseline→6 months):

We hypothesize that intervention participants will report greater increases in trust in the medical profession from baseline to 6 months than control participants; the null hypothesis is that there will be no difference in change between arms.

Self-efficacy (overall; colonoscopy; stool test) and advocacy (baseline→6 months):

We hypothesize that intervention participants will demonstrate greater improvements from baseline to 6 months than control participants; the null hypothesis is that there will be no difference in change between arms.

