9.2 SAMPLE SIZE DETERMINATION

To determine the adequate sample size for our study, we examined achieved power and treatment effects for a study examining the efficacy of a conceptually similar intervention with an equivalent data analysis plan. Specifically, Miller et al. developed a digital decision aid to help patients select a CRC screening test before a primary care appointment. Compared to controls, participants assigned to the decision aid were twice as likely to get screened at 6-month followup (30% [67/223] vs. 15% [34/227], difference=15%, 95% CI 7% to 23%; OR = 2.5). Follow-up analyses with only nonwhite participants continued to show a significant positive effect on screening (34% [33/98] vs. 19% [18/94], difference = 15%, 95% CI 6% to 25%; OR=1.79). Based on the similarity of this research to our own, we anticipate similar screening proportions in our study. To estimate power for the binomial logistic regression analysis on the primary outcome measure (MRR-verified CRC screening), we relied on the sub-analysis from Miller et al.'s data. Importantly, the OR in this analysis (1.79) is consistent with the average effect size of SMS-based interventions on health behaviors (OR=1.81). The G*Power 3.1 program was used to

determine that an odds ratio of 1.79, a two-tailed α error probability of 0.05, and 80% power requires a final sample size of 154 to detect an expected difference in screening rates of 15% at the 6-month follow-up. While unlikely, we will anticipate a conservative 20% attrition rate and set our sample size at 193 (n= 154 post-attrition).

As screening-related health beliefs are important secondary outcomes, we also examined power using treatment effects for screening self-efficacy from the Miller et al. decision aid study. Researchers found that participants in the intervention group reported significantly higher screening self-efficacy (n=223, M=3.89, SD=.84) than control participants (n=227, M=3.64, SD=1.00), $p=.004$. This difference is associated with a Cohen's $d = .27$. To detect a difference of this size in screening self-efficacy, our study will require a final sample size of 110 participants ($\alpha = 0.05$ two-tailed; power = .80). The 154 participants remaining in the analyses post-attrition will be sufficient to detect differences health beliefs across the two survey time points.

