9.4 STATISTICAL ANALYSES

9.4.1 GENERAL APPROACH

Binomial logistic regression will be the main analytic technique for the primary outcome (MRR-verified completion of a recommended CRC screening test). Logistic regression analyses will also examine treatment differences in type of screening received. For secondary outcomes, linear regression will be used. All analyses will control for any confounding variables not managed through randomization (i.e., group difference $p < .10$).

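### Section 9.4.3 does not fix each scale's own baseline score as a covariate; always including it would raise power on the secondary scales by roughly 6 to 12 points over an unadjusted change score

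*Combined protocol and SAP*

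**What the plan says.** Section 9.4.3 is the whole plan for the secondary outcomes. Its model statement is "Linear regression will be used to assess secondary outcomes". Sections 9.4.1, 9.4.3 and 9.4.5 carry the same covariate rule, "All analyses will control for any confounding variables not managed through randomization", defined as a group difference at p < .10. None of them names a scale's baseline score as a standing term, and the variables to be screened are not listed.

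Section 9.1 states each scale hypothesis from baseline to 6 months, for example "the null hypothesis is that there will be no difference in change between arms". Sections 1.3 and 8.1 have the scales measured before randomisation and again at follow-up, so the baseline scores will be in hand.

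For missing scale data, Section 9.4.3 adds "we will conduct multiple imputation for any missing data using the procedures described for the primary outcome". Those procedures are in Section 9.4.2: "Multiple imputation will be based on experimental condition, age at baseline, income, health insurance coverage, and any other covariates predictive of missingness". A scale's baseline score is not named there. It enters only if it predicts missingness.

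Section 9.2 treats health beliefs as important secondary outcomes and concludes: "The 154 participants remaining in the analyses post-attrition will be sufficient to detect differences health beliefs across the two survey time points".

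**The concern.** A scale's baseline score is usually among the best single predictors of its later value. It is known before randomisation and costs nothing further to use. Leaving it to a screening rule means that, in about nine trials out of ten, the rule gives no reason to include it. The arm comparison then carries outcome variance that could have been removed.

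What is at stake is precision on outcomes the protocol itself calls important, in a trial that is small for the effect it assumes. The same gap appears in the imputation model, where the baseline score may be missing from the prediction of the 6-month score.

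**Working it through.** **Inputs.** d = 0.27, two-sided 5% level, 80% power, 154 analysed (77 per arm): Section 9.2. 63 vs 65: Section 1.2. The correlation r between baseline and 6-month score is not given in the documents, so r = 0.3, 0.5 and 0.7 is an assumed range. Scores are taken as normal with equal SD at both times.

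**1. The plan's own figures.** Pooled SD = √[(222 × 0.84² + 226 × 1.00²)/448] = 0.924, so d = 0.25/0.924 = 0.27 and p = 0.004, as stated. The stated requirement of 110 appears with a paired t-test at a standardised difference of 0.27, or with a repeated-measures interaction test at f = 0.135 and r = 0.5. It does not appear for a comparison of two arms without baseline adjustment, which needs 432 (normal formula) or 434 (t-test) in total.

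**2. Variance of the arm comparison,** relative to the 6-month score alone:
- 6-month score alone: 1
- change score: 2(1 − r) = 1.40, 1.00, 0.60
- baseline-adjusted: 1 − r² = 0.91, 0.75, 0.51

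Since 2(1 − r) − (1 − r²) = (1 − r)², the adjusted analysis has the smallest variance for every r between 0 and 1.

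**3. Power,** from the noncentral t with standardised difference 0.27/√(variance factor), full follow-up:

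| Analysis | 63 vs 65, r = 0.3 / 0.5 / 0.7 | 77 per arm, r = 0.3 / 0.5 / 0.7 |
|---|---|---|
| Change, unadjusted | 24.9 / 32.9 / 49.9% | 29.1 / 38.4 / 57.5% |
| 6-month score alone | 32.9% at any r | 38.4% at any r |
| Baseline always included | 35.5 / 41.7 / 56.4% | 41.5 / 48.5 / 64.5% |
| Gain over change (points) | 10.6 / 8.8 / 6.5 | 12.4 / 10.1 / 7.0 |
| Gain over 6-month score (points) | 2.6 / 8.8 / 23.5 | 3.1 / 10.1 / 26.1 |

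**4. Does the p < .10 rule recover the loss?** In 60,000 simulated trials per setting it selected the baseline score in about 10%. Power for the change score under the rule was 24.4 / 33.0 / 50.5% at 63 vs 65 and 29.3 / 38.7 / 58.2% at 77 per arm, almost the same as with no adjustment. With no true effect, the change-score test at 63 vs 65 rejected in 3.6 / 4.0 / 4.4% of trials if the baseline score is screened, and in about 5% if it is not.

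**5. Imputation.** Simulated with 20% missing completely at random, 20 imputations, Rubin's rules, and age, income and insurance taken as unrelated to the scale. Change is analysed under the p < .10 rule except in the last row. Power at r = 0.3 / 0.5 / 0.7:

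| What is imputed, and from what | 128 randomised | 193 randomised |
|---|---|---|
| 6-month score from arm; change then derived | 19 / 22 / 26% | 28 / 32 / 39% |
| 6-month score from arm and baseline; change then derived | 21 / 29 / 41% | 30 / 40 / 59% |
| Change score itself from arm | 22 / 24 / 43% | 28 / 38 / 58% |
| 6-month score from arm and baseline; baseline always in the analysis | 28 / 34 / 46% | 40 / 46 / 63% |

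At r = 0.7, naming the baseline score in the imputation model is worth about 15 points (41 − 26) and 20 points (59 − 39) if the 6-month score is what gets imputed. It is worth almost nothing if the change score is imputed directly. Sections 9.4.2 and 9.4.3 do not say which.

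**The case against.** **The plan is silent; it does not exclude the term.** Section 9.4.3 does not say that a regression of change omits the baseline score, and an analyst could include it. This stands. The supportable claim is that the term is not specified, and the loss arises only if it is left out. But the one rule that is written down would not usually bring it in.

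**The outcome is stated elsewhere.** A reader might infer that the plan leaves the modelled outcome open and quote the gain of about 3 to 26 points over the 6-month score. Section 9.1 words the scale hypotheses as change, so the applicable gain is the 6 to 12 points over a change score. The wider range applies only if the 6-month score alone were modelled.

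**The imputation loss is not a fixed quantity.** A reader might take the 15 to 20 points at r = 0.7 as a general consequence. It holds on one of two readings of which variable is imputed.

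**Removing the p < .10 rule would not help by itself.** Step 4 shows that it hardly moves power for the scales. The rule also governs the primary logistic analysis, for which nothing is computed here, so this point does not ask for it to be replaced there. The status and model of self-reported screening, which Section 9.1 lists as secondary and Sections 3 and 8.1 place within the primary endpoint, is a separate question.

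**Conclusion.** The point holds as a loss of efficiency. Section 9.4.3 does not fix the baseline score, and doing so would add roughly 6 to 12 percentage points of power over an unadjusted change score. The direction is certain for any r between 0 and 1. The size rests on d = 0.27, on full follow-up, and on a correlation that the documents do not give.

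A reader might infer that the planned tests are biased or produce too many false positives. They do not: randomisation makes both the change-score and the adjusted comparison unbiased, and the simulated error rate is at or below about 5%.

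Nor does the change rescue the sample size. Power remains at about 36 to 65%, against the 80% in Section 9.2. Reaching 80% with baseline adjustment would need r of about 0.81 at 154 participants or 0.85 at 128. The mismatch between the stated 110 and a two-arm test is a matter for Section 9.2, and baseline adjustment does not settle it.

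**What to change.** Add to Section 9.4.3:

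> For each continuous scale, the 6-month score is regressed on arm and the baseline score of the same scale, which is always included whatever the baseline arm difference. That baseline score is also always included in the imputation model for the scale.

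With the baseline score in the model, the arm estimate, its standard error and its p-value are the same whether the outcome is the 6-month score or the change. Section 9.1 can therefore stand as written. The added sentence also settles which variable is imputed if it is read as applying to the 6-month score; stating that explicitly would remove the remaining ambiguity.

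The cost is this wording, a dated sign-off and one degree of freedom per model. No new data are needed. Sections 1.2 and 4.1 are partly in the past tense, so the choice should be dated before outcomes are examined by arm. If they have already been examined, the adjusted analysis should be reported as post hoc.

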9.3 POPULATIONS FOR ANALYSES

Because randomization carries the expectation of creating treatment groups equivalent with respect to known and unknown prognostic factors, removing randomized participants from the analysis runs the risk of tampering with this balance and introducing bias into the treatment comparisons. As a result, an intention-to-treat analytic approach will be followed such that all participants randomized into the study will be included in all analyses irrespective of protocol violations post randomization. Even with our best efforts, we can expect some missing data. For the primary outcome, missing data will be limited to cases where we are unable to complete an MRR review. Because we will have medical releases for all participants on our primary outcome, very little missing data is anticipated. For secondary measures, missing data will consist of those who fail to complete the 6-month follow-up survey. We will conduct an initial evaluation of missingness by performing a series of logistic regression analyses where the indicator of missing data is the outcome and potential explanatory variables (e.g., condition, screening status, demographic characteristics) serve as predictors. We will then use imputation to manage missing data.

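### The imputation model for missing 6-month scale scores does not guarantee each scale's own baseline score; leaving it out costs power, and biases the arm comparison only if dropout depends on baseline differently by arm

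*Combined protocol and SAP*

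**What the plan says.** Section 9.4.3 defers to the primary outcome's method: "For the secondary outcomes, we will conduct multiple imputation for any missing data using the procedures described for the primary outcome". Section 9.4.2 describes that method: "Multiple imputation will be based on experimental condition, age at baseline, income, health insurance coverage, and any other covariates predictive of missingness", and "Twenty imputed datasets will be used to provide a combined estimate for missing values". No scale score is named. Section 9.3 gives the variables to be tested as predictors of missingness: "potential explanatory variables (e.g., condition, screening status, demographic characteristics) serve as predictors". These are examples, and none is a scale score.

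The scale hypotheses in section 9.1 are about change. For knowledge: "We hypothesize that intervention participants will show greater improvement in CRC knowledge from baseline to 6 months than control participants"; and for each scale "the null hypothesis is that there will be no difference in change between arms". What will be missing is the later score only: "For secondary measures, missing data will consist of those who fail to complete the 6-month follow-up survey". The baseline survey comes first, according to section 8.1: "After baseline completion, participants are assigned to intervention or control". So the baseline score should be on file for essentially every randomized man.

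Section 9.4.3 names linear regression but does not say whether the outcome is the change score or the 6-month score adjusted for baseline. Both are examined below.

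**The concern.** The borrowed model was written for a binary outcome that has no baseline value. A scale does have one, and a man's own earlier score will usually be the best single predictor of his later one. Under the plan it enters only if it predicts who drops out. That is a different property from predicting the missing score, and it is not the one that recovers information. If the baseline score is left out, each imputed 6-month score is drawn around the arm mean (given age, income and insurance) without regard to where that man started. The imputation model is then narrower than the analysis it feeds.

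Because section 9.3 keeps all randomized men in all analyses, the imputed result is the main result for every scale. At stake are the power of these secondary comparisons and, under one pattern of dropout, their bias.

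**Working it through.** **Plan's own figure.** Section 9.2 inflates 154 for 20% attrition: 154 / 0.80 = 192.5, rounded up to 193. This reproduces. It implies 193 − 154 = 39 scores to impute.

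**Inputs from the documents.** N = 193, allocated 1:1; 20% missing; effect 0.27 SD (section 9.2, self-efficacy); two-sided 5%; 20 imputations.

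**Assumptions.** Scores have SD 1; the baseline-to-6-month correlation ρ is 0.3, 0.5 or 0.7; age, income and insurance are unrelated to the score; where the missingness screen is applied, entry is at p < .05.

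**Variance of the imputed changes.** True variance is 2(1 − ρ) = 1.4 / 1.0 / 0.6. If the imputed score ignores baseline, it is 1 + 1 = 2.0 at every ρ.

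**True precision against complete cases.** Take random dropout, response rate r = 0.8 and many imputations.

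- Change score: imputation without baseline uses the observed 6-month mean minus the full baseline mean, with variance proportional to 1/r + 1 − 2ρ. Complete cases have 2(1 − ρ)/r. The ratios are 1.65/1.75 = 0.94, 1.25/1.25 = 1.00 and 0.85/0.75 = 1.13. Setting the two expressions equal gives ρ = 0.5 for any r.
- Baseline-adjusted: the slope in the completed data shrinks to rρ, and the ratio is (1 − 2r²ρ² + r³ρ²)/(1 − ρ²) = (1 − 0.768ρ²)/(1 − ρ²) = 1.02 / 1.08 / 1.22. It exceeds 1 at every nonzero ρ.

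**Power by simulation.** Bayesian linear-regression imputation, 20 datasets, Rubin's rules, random dropout:

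| Analysis | ρ | Without baseline score | With baseline score | Complete cases |
|---|---|---|---|---|
| Change | 0.3 | 29% | 32% | 29% |
| Change | 0.5 | 35% | 41% | 38% |
| Change | 0.7 | 40% | 59% | 58% |
| Adjusted | 0.3 | 40% | 42% | 43% |
| Adjusted | 0.5 | 44% | 50% | 51% |
| Adjusted | 0.7 | 47% | 64% | 65% |

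With 600 trials, a power near 40% has a simulation error of √(0.4 × 0.6/600) = 2 points. Reruns moved single entries by up to 3 points, so differences of that size between entries should not be over-read.

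Reported SEs for change were 0.193 / 0.175 / 0.155 without the baseline score, 0.185 / 0.159 / 0.125 with it, and 0.190 / 0.161 / 0.125 for complete cases. As a check on the with-baseline column, 0.27/SE − 1.96 is −0.50, −0.26 and +0.20, which gives 31%, 40% and 58%.

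At the schema's N of 128 and ρ = 0.7, power without versus with the baseline score is 26 vs 40% (change) and 32 vs 48% (adjusted).

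All these powers fall below 80%. That is a separate matter: comparing two arm means at d = 0.27 needs 216 men per arm, not 110 in total. The contrast between columns is the point here.

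**Bias.** Suppose low-baseline men drop out more in the experimental arm only, and let δ be the resulting excess in responders' mean baseline. Imputation without baseline is biased by about ρδ; a complete-case change score by −(1 − ρ)δ. Simulated change-score biases were +0.058 / +0.076 / +0.115 and −0.100 / −0.086 / −0.047, so δ is about 0.16. For the adjusted model, imputation without baseline gave +0.05 / +0.08 / +0.12 and complete cases about 0. With the baseline score in the imputation, the change-score bias is at most 0.01.

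**How often the screen would admit the baseline score.** About 3–5% of trials under random dropout, 88–89% if dropout depends on baseline in both arms, and 58–61% if in one arm only (46% at N = 128, ρ = 0.7).

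**The case against.** A reader might infer that the planned imputation is worse than no imputation at all. The documents do not support that as a general statement. For a change score it has the smaller true error when ρ is below 0.5 and the same at 0.5; section 9.4.3 does not say which analysis will be run, and no correlation is given. The statement holds for a baseline-adjusted model, and for change only above 0.5.

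A reader might also infer that the arm comparison is distorted. Arm is in the imputation model, so there is no bias under random dropout, and none beyond simulation error if dropout depends on baseline equally in both arms. One-arm dependence is a scenario that the documents do not predict, and in it a complete-case change score is biased too, in the other direction.

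Much of the increase in reported SE is conservative Rubin variance, not true error. For change, true sampling error rises by only about 2% at ρ = 0.5 (0.1605 vs 0.1567) and 7% at 0.7 (0.1328 vs 0.1242). This stands, but the reported SE drives the test, so the power loss is real. It errs towards missing an effect.

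The missingness clause is a partial route in, since the list in section 9.3 is only illustrative. It works well when dropout depends on baseline in both arms: at ρ = 0.7 the screened model has 57% power for change, against 59% with the score always included. With one-arm dependence the screen reduces the average change-score bias to +0.03 / +0.03 / +0.05 but does not remove it. Under random dropout it almost never helps.

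Finally, section 9.2 calls 20% attrition conservative, and smaller losses shrink every figure here. The borrowed procedures might be read to include the complete-case analysis of section 9.4.2, but that is defined by a known primary outcome and is not clearly carried over to the scales. If the borrowing covers only the software and the number of datasets, the scales have no stated imputation model and still need one.

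**Conclusion.** The concern holds in limited form. Sections 9.4.2 and 9.4.3 leave the most useful predictor of a missing scale score to a screen that selects on a different property. Under random dropout the cost is power alone: 2 to 3 points at ρ = 0.3, 6 at 0.5, and 17 (adjusted) to 19 (change) at 0.7. Bias requires dropout that depends on baseline differently by arm. In the one-arm case examined, leaving the score out gives about +0.06 to +0.12 SD, or 22% to 44% of the planning effect (0.06/0.27 and 0.12/0.27).

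These sizes rest on assumptions not in the documents: the correlation, the dropout patterns, the p < .05 entry rule, and demographics that carry no information about the scale. The MRR-verified primary outcome is not affected. The change is worth making because it is safe under either reading of the secondary regression and costs almost nothing.

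**What to change.** In section 9.4.3, replace the reference to the primary outcome's procedures with a sentence to this effect: each 6-month scale score is imputed from arm, that scale's own baseline score, MRR screening status, age, income and health insurance, whether or not these predict missingness, together with any further variables that do. The other baseline scales may be added but are optional. MRR status is useful because section 9.3 expects it to be known for nearly everyone, including men who miss the follow-up survey. The 20 datasets and the SAS procedures can stay.

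The cost is one SAP sentence and one line of imputation code. No new data are needed.
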